### **4.2 Inclusion Criteria**

Patients will be included in the study only if they meet **all** of the following criteria:

1. Male or female  $\geq$  2 years of age;
2. Have sickle cell disease (confirmed by Hb electrophoresis or more specific tests) or other conditions with iron overload from repeated blood transfusions (see exclusion criteria for exceptions);

3. Baseline LIC >7 mg/g dw (measured by MRI);
4. Patients who have received no less than 20 transfusions of RBCs;
5. Patients who have received at least 1 transfusion per year in the last 2 years and who are expected to have a continuing requirement (based on Investigator's judgement) during the duration of the trial;
6. Patients, and when applicable their legal representatives, will provide a signed and dated written assent/informed consent prior to the first study intervention; patients will be able to adhere to study restrictions, appointments and evaluation schedule.
7. Female patients of childbearing potential must have a negative pregnancy test result at Screening and Baseline Visits. In addition, a female patient of childbearing age who is sexually active must confirm that during the study and for 30 days following the completion of the study or early termination she:
  - will use an effective method of contraception, OR
  - has had a tubal ligation (supporting evidence required), OR
  - has had a hysterectomy (supporting evidence required), OR
  - participates in a non-heterosexual lifestyle, OR
  - indicates her only male sexual partner has been sterilized (supporting evidence required).

Effective methods of contraception include oral contraceptives, intrauterine devices (IUDs) or condom, providing it is used with contraceptive foam or cream, or abstinence from sexual intercourse. Supporting evidence for sterilization consists of a surgical report or letter from the family physician;

8. If the patient is a heterosexual sexually-active fertile male, patient must confirm, in writing, that he and/or his female partner will use an effective method of contraception for the length of the trial and for 30 days following completion of the study or early termination. Effective methods of contraception for males include condoms or sterilization or abstinence from sexual intercourse.

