Dose reduction recommendations will be based on regular assessment of safety markers for adverse reactions that are possibly dose dependent, such as gastrointestinal upset, increases in serum liver enzyme levels, and arthropathies.

Deferoxamine Treatment Arm:

Patients will be prescribed deferoxamine as per the approved US prescribing information at doses of 20 – 40 mg/kg/day for children (<16 years of age) and 40–50 mg/kg/day in adults (≥ 16 years of age) as 8 – 12 h subcutaneous infusion for 5 – 7 days per week. The dose of deferoxamine will be based on the transfusional iron input, on the severity of iron overload at baseline, and on the magnitude of its change during the study.

Deferoxamine 20 mg/kg/day (children) or 40 mg/kg/day (adults):

Patients with transfusional iron input ≤ 0.3 mg/kg/day in the 3 months prior to baseline

AND

Patients with a baseline measure of iron load of:

- Serum ferritin < 2500 $\mu\text{g/L}$

AND

- LIC < 15 mg/g dry weight

AND

- Cardiac T2 > 20 ms

Deferoxamine up to 40 mg/kg/day (children) or 50 mg/kg/day (adults):

Patients with a transfusional iron input > 0.3 mg/kg/day in the 3 months prior to baseline

OR

Patients with at least one baseline measure of iron load as follows:

- Serum ferritin ≥ 2500 $\mu\text{g/L}$

OR

- LIC ≥ 15 mg/g dry weight

OR

- Cardiac T2* ≤ 20 ms

Children (<16 years of age).

The dose of deferoxamine will also be increased up to 40 mg/kg for 5 – 7 days per week at any time during the trial if the mean daily transfusional iron input increases to more than 0.3 mg/kg body weight for at least 3 consecutive months OR at Week 26 if there is less than 10% improvement from baseline to Week 26 in at least one of the measures of iron overload (serum ferritin, cardiac MRI T2* or LIC).

Adults (≥ 16 years of age)

The dose of deferoxamine will be increased up to 50 mg/kg for 5 – 7 days per week at any time during the trial if the mean daily transfusional iron input increases to more than 0.3 mg/kg body weight for at least 3 consecutive months OR at Week 26 if there is less than 10% improvement from baseline to Week 26 in at least one of the measures of iron overload (serum ferritin, cardiac MRI T2* or LIC).

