8.3 Vital Signs, Weight and Height

Descriptive statistics will be presented for temperature, resting heart rate, respiratory rate, systolic blood pressure, diastolic blood pressure, weight and height at each visit. Changes from baseline to each follow-up assessment will be also summarized using descriptive statistics by treatment group.

8.4 12-Lead ECG

ECG data will be summarized using descriptive statistics at each assessment by treatment group. Change from baseline to each follow-up assessment will be also summarized using descriptive statistics by treatment group. Shift tables for clinically significant abnormality between baseline and the last assessment will be constructed by treatment group.

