14.3.3 Weight and Height

Table 14.3.3.1 Weight at each assessment

Table 14.3.3.2 Change in weight from baseline to last assessment

Table 14.3.3.1 Height at each assessment

Table 14.3.3.2 Change in height from baseline to last assessment

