Month 1	xxx	xx.x ± xx.x (xx, xx)	xxx	xx.x ± xx.x (xx, xx)	0.xxxx
Month 2	xxx	xx.x ± xx.x (xx, xx)	xxx	xx.x ± xx.x (xx, xx)	0.xxxx
Month 3	xxx	xx.x ± xx.x (xx, xx)	xxx	xx.x ± xx.x (xx, xx)	0.xxxx
Month 4	xxx	xx.x ± xx.x (xx, xx)	xxx	xx.x ± xx.x (xx, xx)	0.xxxx
...
Month 10	xxx	xx.x ± xx.x (xx, xx)	xxx	xx.x ± xx.x (xx, xx)	0.xxxx
Month 11	xxx	xx.x ± xx.x (xx, xx)	xxx	xx.x ± xx.x (xx, xx)	0.xxxx
Month 12	xxx	xx.x ± xx.x (xx, xx)	xxx	xx.x ± xx.x (xx, xx)	0.xxxx

Note: Similar tables will be produced for resting heart rate, respiration, systolic and diastolic blood pressures.

Data source: 16.2.7 Listing of vital signs including height and weight

Table 14.3.2.2 Change in temperature from baseline to each follow-up assessment

	Treatment				
	Deferiprone		Deferoxamine		
Visit	N	Mean ± SD (Min, Max)	N	Mean ± SD (Min, Max)	P-value (T-test)
Month 1	xxx	xx.x ± xx.x (xx, xx)	xxx	xx.x ± xx.x (xx, xx)	0.xxxx
Month 2	xxx	xx.x ± xx.x (xx, xx)	xxx	xx.x ± xx.x (xx, xx)	0.xxxx
Month 3	xxx	xx.x ± xx.x (xx, xx)	xxx	xx.x ± xx.x (xx, xx)	0.xxxx
Month 4	xxx	xx.x ± xx.x (xx, xx)	xxx	xx.x ± xx.x (xx, xx)	0.xxxx
...
Month 10	xxx	xx.x ± xx.x (xx, xx)	xxx	xx.x ± xx.x (xx, xx)	0.xxxx
Month 11	xxx	xx.x ± xx.x (xx, xx)	xxx	xx.x ± xx.x (xx, xx)	0.xxxx
Month 12	xxx	xx.x ± xx.x (xx, xx)	xxx	xx.x ± xx.x (xx, xx)	0.xxxx

Note: Similar tables will be produced for resting heart rate, respiration, systolic and diastolic blood pressures.

Data source: 16.2.7 Listing of vital signs including height and weight

Table 14.3.3.1 Weight (kg) at each assessment

	Treatment				
	Deferiprone		Deferoxamine		
Visit	N	Mean ± SD (Min, Max)	N	Mean ± SD (Min, Max)	P-value (T-test)
Baseline	xxx	xxx ± xxx (xxx, xxx)	xxx	xxx ± xxx (xxx, xxx)	0.xxxx
Month 1	xxx	xxx ± xxx (xxx, xxx)	xxx	xxx ± xxx (xxx, xxx)	0.xxxx
Month 2	xxx	xxx ± xxx (xxx, xxx)	xxx	xxx ± xxx (xxx, xxx)	0.xxxx
Month 3	xxx	xxx ± xxx (xxx, xxx)	xxx	xxx ± xxx (xxx, xxx)	0.xxxx
Month 4	xxx	xxx ± xxx (xxx, xxx)	xxx	xxx ± xxx (xxx, xxx)	0.xxxx
...
Month 10	xxx	xxx ± xxx (xxx, xxx)	xxx	xxx ± xxx (xxx, xxx)	0.xxxx
Month 11	xxx	xxx ± xxx (xxx, xxx)	xxx	xxx ± xxx (xxx, xxx)	0.xxxx
Month 12	xxx	xxx ± xxx (xxx, xxx)	xxx	xxx ± xxx (xxx, xxx)	0.xxxx

Data source: 16.2.7 Listing of vital signs including height and weight

Table 14.3.3.2 Change in weight from baseline to last assessment

		Treatment		
		Deferiprone	Deferoxamine	
N		xxx	xxx	P-value (T-test)

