Change in weight (kg) Mean ± SD (Min, Max)	Baseline	xxx.x ± xxx.x (xxx, xxx)	xxx.x ± xxx.x (xxx, xxx)	0.xxxx
	Last assessment	xxx.x ± xxx.x (xxx, xxx)	xxx.x ± xxx.x (xxx, xxx)	0.xxxx
	Change at last assessment	xxx.x ± xxx.x (xxx, xxx)	xxx.x ± xxx.x (xxx, xxx)	0.xxxx

Data source: 16.2.7 Listing of vital signs including height and weight

Table 14.3.3.1 Height (cm) at each assessment

		Treatment			
		Deferiprone	Deferoxamine		
Visit	N	Mean ± SD (Min, Max)	N	Mean ± SD (Min, Max)	P-value (T-test)
Baseline	xxx	xxx ± xxx (xxx, xxx)	xxx	xxx ± xxx (xxx, xxx)	0.xxxx
Week 26	xxx	xxx ± xxx (xxx, xxx)	xxx	xxx ± xxx (xxx, xxx)	0.xxxx
Week 52	xxx	xxx ± xxx (xxx, xxx)	xxx	xxx ± xxx (xxx, xxx)	0.xxxx

Data source: 16.2.7 Listing of vital signs including height and weight

Table 14.3.3.4 Change in height from baseline to last assessment

		Treatment		
		Deferiprone	Deferoxamine	
N		xxx	xxx	P-value (T-test)
Height (cm): Mean ± SD (Min, Max)	Baseline	xxx.x ± xxx.x (xxx, xxx)	xxx.x ± xxx.x (xxx, xxx)	0.xxxx
	Last assessment	xxx.x ± xxx.x (xxx, xxx)	xxx.x ± xxx.x (xxx, xxx)	0.xxxx
	Change at last assessment	xxx.x ± xxx.x (xxx, xxx)	xxx.x ± xxx.x (xxx, xxx)	0.xxxx

Data source: 16.2.7 Listing of vital signs including height and weight

Table 14.3.4.1 Concomitant medications

	Treatment		
	Deferiprone (N)	Deferoxamine (N)	
Exposure (patient-years): x.xx		Exposure (patient-years): x.xx	
Total Patients Reporting: xx		Total Patients Reporting: xx	
Preferred Name	n Patients (%)		n Patients (%)
ccccc	x (x.x)		x (x.x)
ccccc	x (x.x)		x (x.x)
ccccc	x (x.x)		x (x.x)
.....

Data source: 16.2.26 Listing of medication

Table 14.3.5.1 Heart rate of 12-lead ECG at each assessment

	Treatment				
Heart Rate (bpm)	Deferiprone		Deferoxamine		P-value (T-test)
	N	Mean \pm SD (Min, Max)	N	Mean \pm SD (Min, Max)	
Baseline	xxx	xx.x \pm xx.x (xx, xx)	xxx	xx.x \pm xx.x (xx, xx)	0.xxxx
Month 6	xxx	xx.x \pm xx.x (xx, xx)	xxx	xx.x \pm xx.x (xx, xx)	0.xxxx
Month 12	xxx	xx.x \pm xx.x (xx, xx)	xxx	xx.x \pm xx.x (xx, xx)	0.xxxx

Note: Similar tables will be produced for PR (ms), QRS (ms), QT (ms), QTcF (ms), and QTcB (ms), respectively.

Data source: 16.2.9 Listing of 12-lead electrocardiogram

Table 14.3.5.2 Change in heart rate of 12-lead ECG at each follow-up assessment

Heart Rate (bpm)	Treatment				P-value (T-test)
	Deferiprone	Deferoxamine	N	Mean ± SD (Min, Max)	
Month 6	xxx	xx.x ± xx.x (xx, xx)	xxx	xx.x ± xx.x (xx, xx)	0xxxx
Month 12	xxx	xx.x ± xx.x (xx, xx)	xxx	xx.x ± xx.x (xx, xx)	0xxxx

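### Height and weight change are pooled from age 2 to adult in raw cm and kg, which dilutes any effect confined to growing patients

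*SAP*

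**What the plan says.** **Who is enrolled.** Protocol 4.2 admits "Male or female $\geq$ 2 years of age" and sets no upper age limit. Children are expected: deferoxamine dosing has its own range below 16 (SAP 3.3), and the Child Health Questionnaire is used up to age 17 (Protocol 8.1.2.1). Randomisation is stratified by disease category and prior transfusional iron input, not by age (Protocol 4.9, SAP 3.6).

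**How height and weight are analysed.** SAP 8.3 asks for descriptive statistics at each visit and adds: "Changes from baseline to each follow-up assessment will be also summarized using descriptive statistics by treatment group". The shells in SAP 17 set the scale, with "Table 14.3.3.1 Weight (kg) at each assessment" and "Table 14.3.3.1 Height (cm) at each assessment". Both show mean, SD and range by arm with a t-test p-value. The change tables have the same layout. The table list in SAP 14.3.3 gives "Table 14.3.3.2 Change in weight from baseline to last assessment", and the height counterpart is "Change in height from baseline to last assessment" (numbered 14.3.3.4 in the shells).

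**What is absent.** The only safety split is sickle cell disease against other anemias (SAP 8). Neither document plans an age group, standardised score, percentile or growth velocity for these measures. Height is measured at screening/baseline, Week 26 and Week 52 (SAP Table 1, note 5).

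**The concern.** Over 52 weeks, height changes materially only in patients who are still growing. A mean that mixes growing children with adults therefore mainly reports how many children the arm contains. If one drug slowed growth, the pooled table would show only the child share multiplied by the effect, against a spread made up mostly of the age mix. A non-significant pooled p-value could then be read as reassurance about growth in children when it carries little information.

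Weight has some link to known experience. The adverse event table in Protocol 1.2 lists weight increased (1.9%) and increased appetite (4.0%) with deferiprone. In children, ordinary growth sits on top of any such effect.

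There is also a mismatch over timing. SAP 8.3 promises change at every follow-up assessment, and the Protocol's vital-signs analysis (11.4.1.4) likewise plans change to each post-baseline time point for weight. The change shells show only the last assessment, whenever that fell.

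**Working it through.** The plan states no power or sample size for height or weight, so there is no figure to reproduce. What follows illustrates size on assumed inputs.

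**Inputs from the documents.** 142 deferiprone and 71 deferoxamine patients (SAP sample size text, before section 3.3).

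**Assumed inputs.** Child share f = 0.3, 0.5 or 0.7; child growth 6 cm/year, SD 2; adult change 0, SD 0.5; growth lower by 1.5 cm/year in one arm's children; two-sided 5% test, normal approximation.

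**Pooled test.** Variance = f×2² + (1−f)×0.5² + f(1−f)×6². SE = SD × √(1/142 + 1/71) = SD × 0.1453. Expected difference = 1.5f.

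| f | Variance | SD | SE | Difference (cm) | Power |
|---|---|---|---|---|---|
| 0.3 | 1.2 + 0.175 + 7.56 = 8.935 | 2.99 | 0.434 | 0.45 | 18% |
| 0.5 | 2.0 + 0.125 + 9.00 = 11.125 | 3.34 | 0.485 | 0.75 | 34% |
| 0.7 | 2.8 + 0.075 + 7.56 = 10.435 | 3.23 | 0.470 | 1.05 | 61% |

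The age-mix term supplies 7.56/8.935 = 85%, 9/11.125 = 81% and 7.56/10.435 = 72% of the pooled variance.

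**Children only.** SE = 2 × √(1/(142f) + 1/(71f)) = 0.531, 0.411 and 0.347. The difference is 1.5 cm. Power is 81%, 95% and 99%.

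**Chance age imbalance.** The SD of the between-arm difference in child share is √(f(1−f)(1/142 + 1/71)) = 6.7 to 7.3 percentage points. At 6 cm/year that is 0.40 to 0.44 cm of random arm difference.

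**Level and dilution by simulation.** The planned t-test was simulated at 142:71 (4,000 runs; 1,000 for the children-only rejection rates), with child growth of 4 or 6 cm/year.

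- No drug effect: the arm difference averages 0 and the test rejects in 4.6% to 5.6% of runs. Mean height change in an arm still runs from 1.2 cm (30% children, 4 cm/year) to 4.2 cm (70%, 6 cm/year).
- 1 cm slowing in children: the pooled estimate is 0.3 to 0.7 cm, with power 13% to 54% and the wrong sign in 2% to 24% of runs. Children-only power is 44% to 83%.
- 2 cm slowing: the pooled estimate is 0.6 to 1.4 cm, with power 39% to 99%. Children-only power is 94% to 100%.

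**Weight.** Assume a gain of 3 kg/year (SD 2.5) in children and 0.5 (SD 3.5) in adults. A 2 kg effect confined to children has power 25%, 60% or 90% pooled, against 84%, 97% or 100% in children alone, for f = 0.3, 0.5 or 0.7. An effect equal at all ages is not diluted.

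**Last assessment.** At 6 cm/year, a child last measured at Week 26 contributes 6 × 26/52 = 3 cm to the change table, and one measured at Week 52 contributes 6 cm.

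**The case against.** A reader might infer that the tables would misreport a growth or weight effect, or that the comparison is confounded by age. The documents do not support that. Patients are randomised, so age mix adds noise and not systematic bias, and the pooled SD already contains that noise. This is why the simulated test keeps its level. The one qualification is follow-up: change to the last assessment is comparable only if time in study is similar in the two arms.

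Other parts of the defence also stand. Ordinary weight gain in children is added to both arms and cancels in expectation, and an effect in adults shows directly. Weight increased and increased appetite are adverse event terms that the planned adverse event tables already compare by arm. The adverse event material in Protocol 1.2 and 1.3 names no growth effect for either drug, so the 1.5 cm/year loss is purely illustrative. Height and weight are not listed safety endpoints (Protocol 11.2.3), and the Protocol's vital-signs analysis omits height.

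Nor is it right to infer that the trial could not report growth in children at all. Patient listings hold demographics, height and weight (SAP 16.2), SAP 7.6 allows post hoc exploratory analyses, and SAP 17 allows the shells to vary.

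What this leaves standing is that listings do not compare arms, and an age-specific table chosen after the results are seen carries less weight than a planned one. The fix also has limits: for a 1 cm slowing, even the children-only comparison has 44% to 83% power.

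**Conclusion.** The point holds as one of dilution and lost power. The pooled height comparison is valid as a test but poorly aimed. The mean change in each arm mostly reflects the share of children, and an effect confined to growing patients is scaled down by that share. On the assumed inputs, pooled power for a 1.5 cm/year effect is 18%, 34% or 61%, against 81%, 95% or 99% in children alone.

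Child share, growth rates, SDs and effect size are all assumptions. The documents give no age distribution, so the true size cannot be fixed from them. The children-only figures are for raw cm, not standardised scores. The point is weaker for weight.

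The mismatch between the text of SAP 8.3 and the last-assessment shells rests on no assumption and needs correcting in any case. Severity is low: these are supporting safety summaries, and no clinical-management rule is involved.

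**What to change.** In SAP 8.3 and the 14.3.3 tables and shells:

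1. Report height and weight change by age group, for example under 16 and 16 or over. That is the cut used for deferoxamine dosing. The quality-of-life instruments divide at 17/18, so the choice should be stated.
2. For patients still growing, add change in age- and sex-standardised height and weight at Weeks 26 and 52 by arm, using one growth reference named in advance.
3. Do not rely on the pooled height-change t-test.
4. Reconcile the 8.3 text with the shells by showing change at the fixed visits. Any last-assessment table that is kept should be labelled as such.

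Age, sex, height and weight are already collected, so no new data are needed and the primary analysis is untouched. The cost is a few more tables, fewer patients per group, and the choice of a growth reference, which the documents do not name.

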### 4.3 Exclusion Criteria

Patients will be excluded from the study for **any** of the following reasons:

1. Thalassemia syndromes;
2. Myelodysplastic syndrome (MDS) or myelofibrosis;
3. Diamond Blackfan anemia;
4. Primary bone marrow failure;

5. Patients with a baseline LIC >30 mg/g dw (measured by MRI);
6. Unable or unwilling to undergo a 7-day washout period if currently being treated with deferiprone or deferoxamine or deferasirox;
7. Previous discontinuation of treatment with deferiprone or deferoxamine due to adverse events;
8. History or presence of hypersensitivity or idiosyncratic reaction to deferiprone or deferoxamine;
9. Treated with hydroxyurea within 30 days;
10. History of malignancy;
11. Evidence of abnormal liver function (serum ALT level(s) > 5 times upper limit of normal at screening or creatinine levels >2 times upper limit of normal at screening);
12. A serious, unstable illness, as judged by the Investigator, during the past 3 months before screening/baseline visit including but not limited to: hepatic, renal, gastro-enterologic, respiratory, cardiovascular, endocrinologic, neurologic or immunologic disease.
13. Clinically significant abnormal 12-lead ECG findings;
14. Cardiac MRI T2\* <10 ms
15. Myocardial infarction, cardiac arrest or cardiac failure within 1 year before screening/baseline visit;
16. Bowel disease causing malabsorption;
17. HIV positive patient;
18. Unable to undergo MRI;
19. Presence of metallic objects such as artificial joints, inner ear (cochlear) implants, brain aneurysm clips, pacemakers, and metallic foreign bodies in the eye or other body areas that would prevent use of MRI imaging;
20. History of alcohol or drug abuse;
21. Treatment with an investigational drug within 30 days or 5 half-lives (whichever is longer) preceding the first dose of study medication;
22. Participation in another clinical trial during the conduct of this study;
23. Pregnant, nursing females and females of childbearing potential who are sexually active and unwilling, or unable, to use an acceptable method of contraception;
24. Mental incapacity, unwillingness or language barriers precluding adequate understanding or co-operation;
25. Any condition that, in the opinion of the Investigators, would adversely affect ability to complete the study or its assessments.

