## 4.4 Enrolment Violations

The criteria for enrolment must be followed explicitly. If there is inadvertent enrolment of patients who do not meet enrolment criteria, such patients should be withdrawn from the study.

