### **8.2.3 ECG**

A standard 12-lead ECG will be performed at the screening, Week 26, and end of study (Week 52 or early termination) visits. As a minimum, the following parameters will be assessed: HR, PR, QRS, QT, QTcF, and QTcB. Results will be interpreted by the Investigator. The overall interpretation will also be documented.

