#### ECGs

Clinically significant 12-lead ECG abnormalities will be reported. The number and percentage of patients with normal and abnormal 12-lead ECG results will be provided for each scheduled visit.

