## CLINICAL STUDY PROTOCOL

STUDY CODE: LA38-0411

STUDY PROCEDURE	Baseline Phase				Treatment Phase			
	Screening/ Baseline	Baseline	Hematology Assessments 	Telephone Calls (Week 1, 2, 3)	Monthly Visits (Week 4, 8, 16, 20, 32, 36, 44, 48)	Quarterly Visits (Week 12, 40)	Semi-Annual Visit (Week 26)	End of Study / Early Termination Visit  (Week 52)
Quality of Life Questionnaire (SF-36/ Child Health Questionnaire)		X					X	X
Serum Ferritin		X				X	X	X
Liver MRI/LIC	X 						X	X
Cardiac MRI T2*	X 						X	X
Dose Calculation/Verify and adjust dose level		X			X	X	X	
Contact IVRS/IWRS		X			X	X	X	X
Dispense study medication		X			X	X	X	
Dispense Patient Diary Card		X			X	X	X	
Review and Collect Diary Card					X	X	X	X
Medical events/Adverse events	X	X		X	X	X	X	X
Concomitant medications				X	X	X	X	X
Transfusion information (if applicable) 			X		X	X	X	X
Return used and unused study medication					X	X	X	X

X- To do, V- To verify, R- To review

1. Hematology testing is to be done weekly up to Week 26 and biweekly thereafter.
2. Early Termination: if patient withdraws from the study prior to Week 52, the patient must be seen for an early termination visit.
3. These evaluations must be done within 14 days prior to baseline visit. Females of childbearing potential must be making use of an approved birth control method at least one month prior to starting study medication.
4. Results from these tests will be considered the baseline values.
5. Height will only be measured at screening/baseline, semi-annual and Week 52 visits.
6. These evaluations must be conducted within two months prior to starting study medication
7. Collect volume of blood that the patient received during the transfusion and the mean hematocrit of the packed red blood cell units transfused.

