Note: Similar tables will be produced for PR (ms), QRS (ms), QT (ms), QTcF (ms), and QTcB (ms), respectively.

Data source: 16.2.9 Listing of 12-lead electrocardiogram

Table 14.3.5.3 Shift table for clinically significant abnormality for 12-lead ECG: Deferiprone group

	n (%)	Last Assessment		P-value (McNemar's test)
		Normal	Abnormal	
Baseline	Normal	xx (xx)	xx (xx)	0xxxx
	Abnormal	xx (xx)	xx (xx)	

P-value = Data source: 16.2.9 Listing of 12-lead electrocardiogram

Table 14.3.5.4 Shift table for clinically significant abnormality for 12-lead ECG: Deferoxamine group

	n (%)	Last Assessment		P-value (McNemar's test)
		Normal	Abnormal	
Baseline	Normal	xx (xx)	xx (xx)	0xxxx
	Abnormal	xx (xx)	xx (xx)	

P-value = Data source: 16.2.9 Listing of 12-lead electrocardiogram

Table 14.3.6.1.1 Hemoglobin at each assessment

	Treatment				P-value (T-test)
	Hemoglobin	Deferiprone		Deferoxamine	
Visit	N	Mean ± SD (Min, Max)	N	Mean ± SD (Min, Max)	0.xxxx
Baseline	xxx	xx.x ± xx.x (xx, xx)	xxx	xx.x ± xx.x (xx, xx)	0.xxxx
Week 1	xxx	xx.x ± xx.x (xx, xx)	xxx	xx.x ± xx.x (xx, xx)	0.xxxx
Week 2	xxx	xx.x ± xx.x (xx, xx)	xxx	xx.x ± xx.x (xx, xx)	0.xxxx
Week 3	xxx	xx.x ± xx.x (xx, xx)	xxx	xx.x ± xx.x (xx, xx)	0.xxxx
Week 4	xxx	xx.x ± xx.x (xx, xx)	xxx	xx.x ± xx.x (xx, xx)	0.xxxx
...
Week 49	xxx	xx.x ± xx.x (xx, xx)	xxx	xx.x ± xx.x (xx, xx)	0.xxxx
Week 50	xxx	xx.x ± xx.x (xx, xx)	xxx	xx.x ± xx.x (xx, xx)	0.xxxx
Week 51	xxx	xx.x ± xx.x (xx, xx)	xxx	xx.x ± xx.x (xx, xx)	0.xxxx
Week 52	xxx	xx.x ± xx.x (xx, xx)	xxx	xx.x ± xx.x (xx, xx)	0.xxxx

Note: Similar tables will be produced for total white blood cell (WBC), absolute neutrophil count (ANC), and platelets.

Data source: 16.2.11 Listing of hematology

Table 14.3.6.1.2 Change in hemoglobin at each follow-up assessment

	Treatment				
	Hemoglobin	Deferiprone		Deferoxamine	
Visit	N	Mean ± SD (Min, Max)	N	Mean ± SD (Min, Max)	0xxxx
Week 1	xxx	xx.x ± xx.x (xx, xx)	xxx	xx.x ± xx.x (xx, xx)	0xxxx
Week 2	xxx	xx.x ± xx.x (xx, xx)	xxx	xx.x ± xx.x (xx, xx)	0xxxx
Week 3	xxx	xx.x ± xx.x (xx, xx)	xxx	xx.x ± xx.x (xx, xx)	0xxxx
Week 4	xxx	xx.x ± xx.x (xx, xx)	xxx	xx.x ± xx.x (xx, xx)	0xxxx
...
Week 49	xxx	xx.x ± xx.x (xx, xx)	xxx	xx.x ± xx.x (xx, xx)	0xxxx
Week 50	xxx	xx.x ± xx.x (xx, xx)	xxx	xx.x ± xx.x (xx, xx)	0xxxx
Week 51	xxx	xx.x ± xx.x (xx, xx)	xxx	xx.x ± xx.x (xx, xx)	0xxxx
Week 52	xxx	xx.x ± xx.x (xx, xx)	xxx	xx.x ± xx.x (xx, xx)	0xxxx

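### The within-arm McNemar p-values for ECG shift can point only to worsening, mix incidence with arm size, and say nothing about one arm against the other

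*SAP*

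**What the plan says.** SAP 8.4 (12-Lead ECG) states: "Shift tables for clinically significant abnormality between baseline and the last assessment will be constructed by treatment group". It names no test. The test appears only in SAP section 17, in the shell titled "Table 14.3.5.3 Shift table for clinically significant abnormality for 12-lead ECG: Deferiprone group" and its deferoxamine twin, Table 14.3.5.4. Each is a two-by-two table of baseline against last assessment within one arm, with a final column that begins "P-value (McNemar's test".

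Three protocol provisions determine what can appear in those tables:

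- Section 4.3, item 13, excludes patients with "Clinically significant abnormal 12-lead ECG findings".
- Section 8.2.3 sets the ECG times: "A standard 12-lead ECG will be performed at the screening, Week 26, and end of study (Week 52 or early termination) visits". On Day 0 the schedule in Appendix 18.1 asks only that the ECG be verified. The screening ECG carries footnote 4: "Results from these tests will be considered the baseline values". SAP Table 1 repeats this.
- Section 4.4 deals with patients enrolled in error: "If there is inadvertent enrolment of patients who do not meet enrolment criteria, such patients should be withdrawn from the study".

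For ECG reporting, Protocol 11.4.1.4 asks for something else: "The number and percentage of patients with normal and abnormal 12-lead ECG results will be provided for each scheduled visit". The SAP table list (14.3.5) has by-visit tables only for heart rate and the ECG intervals. Its only categorical ECG tables are the two shift tables.

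**The concern.** McNemar's test weighs shifts in one direction against shifts in the other. Here eligibility has already fixed one direction at about zero, because the ECG that admits the patient is also the baseline ECG. The null hypothesis of equal abnormality rates before and after can then hold only if nobody ever develops an abnormality. A small p-value shows no more than that several patients did so over a year. It cannot separate a drug effect from background change in this population, because no control arm enters the test.

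Allocation is 2:1, so the same incidence gives about twice the count in the deferiprone arm and a much smaller p-value there. The 12-lead ECG is a named safety endpoint (Protocol 11.2.3). Two tables printed side by side, one significant and one not, invite a comparison that neither table makes.

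Using only the last assessment also loses an abnormality seen at Week 26 that has gone by Week 52.

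**Working it through.** The plan states no sample size, power or significance level for this test, so there is no figure of its own to reproduce.

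**Inputs from the documents.** Projected interim arm sizes are 142 deferiprone and 71 deferoxamine (SAP, sample size section). The tables are 2 × 2 within each arm (SAP section 17).

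**Assumptions.** True incidence of a new clinically significant abnormality ranges from 1% to 10% and is equal in both arms. The significance level is 0.05. All patients have a post-baseline ECG. The SAP does not say whether McNemar is exact or asymptotic, so both are shown.

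**Formula.** Let *b* be normal-to-abnormal shifts and *c* abnormal-to-normal shifts.

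- Exact: p = 2 × P(Bin(b + c, 0.5) ≤ min(b, c)). With c = 0 this is p = 2^(1−b).
- Uncorrected chi-square: (b − c)²/(b + c). With c = 0 this equals b.

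Exact p-values with c = 0: b = 3 gives 0.25; 4 gives 0.125; 5 gives 0.0625; 6 gives 0.031; 8 gives 0.008. So exact p < 0.05 needs b ≥ 6, which is 6/142 = 4.2% of one arm but 6/71 = 8.5% of the other. The uncorrected chi-square needs b ≥ 4: 4/142 = 2.8% against 4/71 = 5.6%.

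**Chance of p < 0.05 when the true incidence is the same in both arms** (binomial probability of b ≥ 6 for exact, b ≥ 4 for chi-square):

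| Incidence | Exact, n = 142 | Exact, n = 71 | Chi-square, n = 142 | Chi-square, n = 71 |
|---|---|---|---|---|
| 1% | 0.003 | 0.000 | 0.055 | 0.006 |
| 2% | 0.067 | 0.003 | 0.317 | 0.054 |
| 3% | 0.255 | 0.020 | 0.619 | 0.164 |
| 5% | 0.719 | 0.144 | 0.928 | 0.477 |
| 8% | 0.974 | 0.506 | 0.997 | 0.829 |
| 10% | 0.997 | 0.726 | 1.000 | 0.933 |

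**Two hypothetical outcomes:**

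- Equal rates, 8/142 and 4/71 (5.6% each): exact McNemar p = 0.008 and 0.125; Fisher's exact test between arms p = 1.0.
- Unequal rates, 3/142 (2.1%) and 8/71 (11.3%): exact McNemar p = 0.25 and 0.008; Fisher p = 0.007.

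**Edge cases.** If an arm has no new abnormality, the chi-square statistic is 0/0 and undefined. One enrolment violation that shifts to normal (c = 1) raises the exact requirement: b = 6 gives 0.125, b = 7 gives 0.070, b = 8 gives 0.039.

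**The case against.** A reader might infer that the p-value reflects arm size and not drug effect. The documents do not support that. With c = 0 the p-value is driven by incidence times arm size, so a drug effect on incidence does move it. In the 3/142 against 8/71 example the smaller arm has the smaller p-value.

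A reader might also infer that the trial has no between-arm look at ECG safety. That is wrong too. Protocol 8.2.4.2 requires clinically significant ECG abnormalities that meet the adverse-event definition, and are not part of a condition already recorded, to be entered as adverse events. SAP Table 14.3.1.2 compares adverse events between arms by Fisher's exact test. That route would also catch a Week 26 finding that later resolves. Tables 14.3.5.1 and 14.3.5.2, with their companion tables for the intervals, compare heart rate, PR, QRS, QT, QTcF and QTcB by t-test at Months 6 and 12. The adverse-event route does spread ECG findings over preferred terms, so it gives no single count per arm.

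The defence can add that nothing acts on this p-value. SAP section 6 sets 0.05 for disposition and baseline characteristics only; section 8 calls for frequency tables for discrete safety data; section 17 says the shells may change; and no stopping or efficacy rule uses the test. At 2% incidence the exact test would usually be non-significant in both arms. All of this stands and limits the consequence. None of it makes the McNemar p-value informative.

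Finally, the baseline-abnormal row may not be wholly empty. A patient enrolled in error and dosed stays in the Safety population. The shells also label their rows only normal and abnormal. If any abnormality were counted, the row would fill, but the tables would contradict their own titles.

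**Conclusion.** The point holds, as a minor one. As titled, the two tables test a change that eligibility allows in only one direction. Their p-values depend on the count of new abnormalities alone and provide no evidence between arms. With equal true incidence of 2%, 5% or 10%, exact p < 0.05 occurs with probability 0.07, 0.72 or about 1.00 on deferiprone and 0.003, 0.14 or 0.73 on deferoxamine. These figures rest on the assumed incidences, the assumed 0.05 level, the exact form of the test, the projected interim arm sizes, and no enrolment violations.

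The effect stays within descriptive safety tables. It does not reach the primary analysis or any decision rule. Separately, the per-visit normal and abnormal counts required by Protocol 11.4.1.4 are missing from the SAP table list, and that is a plain mismatch between the two documents.

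**What to change.** 1. Remove the McNemar p-value from the shells of Tables 14.3.5.3 and 14.3.5.4.
2. State in both shells that abnormal means clinically significant abnormal, as the titles say.
3. In SAP 8.4, add by arm the number and percentage of patients with any new clinically significant ECG abnormality at any post-baseline ECG (Week 26, Week 52 or early termination). If the arms are to be compared, use Fisher's exact test or a difference in proportions with a confidence interval.
4. Add to SAP 14.3.5 the normal and abnormal counts and percentages at each scheduled visit.

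The cost is SAP wording, two revised shells, and tables for the new-abnormality and per-visit counts. The ECGs are already collected, so no new data are needed.
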